Aim 1. Pilot test a TIC-adapted ACP intervention with UHS residents in an affordable housing-located resiliency hub for initial efficacy, based on outcomes of ACP values/beliefs, processes (e.g., looking up ACP information), and actions (e.g., advance directive completion, family conversations about life-sustaining measures). We will enroll a cohort of UHS residents (n=30) to assess baseline ACP status, Adverse Childhood Experiences, and previous death-related experiences and deliver an intervention that is sensitive to past trauma following a novel standardized ACP checklist developed from a narrative synthesis of ACP conversation guides [1]. *H1: We hypothesize the intervention will decrease misconceptions about ACP (ACP values/beliefs), increase ACP processes, and increase ACP actions (e.g., advance directive completion, family conversations about life-sustaining measures).*

Aim 2. Assess intervention acceptability, appropriateness, and feasibility among residents and preliminary barriers and facilitators to implementation. Anticipated barriers and facilitators may include identifying peers and staff to facilitate ACP discussions; document management and retention; dedicating time and space to intervention delivery vs. addressing critical social determinants of health (e.g., transportation, food, healthcare), and long-term decisional support as ACP preferences change with life and health events. In addition to the residents completing a brief implementation outcomes survey, we will hold audio-recorded 15-minute debriefs with residents following the intervention to assess process concerns and barriers and facilitators. *H2: We hypothesize that UHS residents (n=30) will find the intervention to be acceptable, appropriate, and feasible.*

B. Background and Significance

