
C. Preliminary Studies

During the summer of 2020, [name] conducted five qualitative interviews with Nashville affordable housing specialists to hone the approach for her dissertation study protocol and learn more about the population of interest. Following her dissertation, she identified that structural, life-stage, and social stressors and resources strongly influence individual stress responses and ACP motivation, which in turn affects ACP preferences and practices (**Figure 2**). The findings also emphasized the importance of trust and a general history of disenfranchisement. This finding reinforced the plan to use trusted

community partnerships, face-to-face study interactions to promote rapport, and emphasized the investigator's reliance on participant expertise to fuel the proposed study. Resident illiteracy was also major finding from these interviews and influenced the choice of investigator-administered study instruments. This work informed variable selection for the ongoing R4R study (September 2023–June 2025): healthcare access and quality, resilience, coping, and adverse/positive childhood experiences. [name] is serving as a Co-Investigator on the R4R study and overseeing all study ACP measures. After piloting the R4R questionnaire with 15 residents of one of UHS's sites

Figure 2. Conceptual framework of cumulative resources and stressors, individual stress responses, and advance care planning outcomes.

in September 2023, 8/15 (53%) stated they would be “very interested” in a center that provides “end-of-life planning” and 73.3 % (11/15) were “very interested” in a center that provides medical or legal planning. Although eight (53.3%) stated they had heard of ACP before, most respondents (13/15, 86.7%) had not completed an advance directive, only 7/15 (46.7) had informally identified a healthcare decision-maker, 6/15 (40%) had discussed life-sustaining measures and quality of life with family, and only 3/15 (20%) had discussed ACP with their doctor. These numbers underscore the **significant need for adaptive and early intervention** to explore patient planning needs, carefully screen for trauma and adapt approach to trauma needs, and foster appropriate follow-up for patients. The R4R Study preliminary data and procedures will inform ongoing intervention development for this proposed study.

D. Research Design and Methods

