TIC principles: safety, trustworthiness and transparency, peer support, collaboration and mutuality, empowerment, and choice, and cultural, historical, and gender issues [23-25]. Adverse Childhood Experiences and previous death-related experiences assessed during baseline data collection will be used to tailor the discussion to carefully explore relevant history to assess resident ACP values, preferences, and goals. Participants will be offered the opportunity to complete an advance directive, but some participants may not be ready for this step, as follow-up questions may arise for additional family, friends, or provider discussion. Following each intervention session, the PI will hold a fifteen- to twenty-minute, audio-recorded discussion to review the intervention for possible adaptations to align it with TIC principles and barriers and facilitators (Aim 2). While peer support will not be used in this intervention, participants will be asked for suggestions of how to involve peers to facilitate the ACP process.

D3. Eligibility. Inclusion criteria for enrollment in the intervention will include an adult (18+) residing in a UHS unit that does not have a completed advance directive and exclusion criteria include inability to provide informed consent or participate in the intervention due to cognitive, auditory, visual impairment or non-English language barrier.

D4. Recruitment and enrollment. We will purposively sample from one of UHS’s properties. Participant selection will start with R4R study participants that communicated interest in future study participation and non-participants that were interested, but unable to participate in the study due to randomized selection. Residents will be contacted by phone, text, or door knocking depending on their communication preference and availability of contact information from the R4R study. If the individual does not answer the door, a letter and flyer will be left at the door with the contact information of the study team. We also will post study flyers in common spaces to advertise the study. **To promote a diverse sample, we will stratify by age (1 are 18 to 39, 14 are 40 to 59, and 15 are 60+), 16-20 identify as Black or African American, and 16-20 identify as male.** If eligible (inclusion criteria are met, and no exclusion criteria are present), the PI or Key Study personnel (KSP) will set a time to meet in person or remotely to

[figure not shown]
Table 1. Standardized ACP Checklist

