D5.2 Data collection procedures. During Visit 1 and Visit 3, the questionnaire will be administered to each participant in-person by the study team member. For in-person questionnaire administration, a copy of the questions and responses will be available to the participant to reference. The KSP will enter participant responses directly into REDCap using a tablet computer. If internet is inaccessible, responses will be recorded on paper using the participant's study ID. If in-person procedures are not possible, but the participant has access to a computer and internet (i.e., to complete e-consent), and a telephone, interviews will be completed remotely by telephone. The Visit 1 questionnaire procedures will take approximately 45 minutes and the Visit 3 questionnaire of fewer items will take approximately 30 minutes. Qualitative Debrief Interview: The PI will complete the intervention and then commence the 15-20-minute audio-recorded interview using a semi-structured interview guide. This interview will focus on the participant's perceptions of the intervention, any moments of discomfort, stress, or discomfort, and suggestions for how to align the intervention with TIC principles (e.g., how can we make you feel safer during this discussion).

Intervention Fidelity: Members of the PI's mentor team or a peer at the Vanderbilt University School of Nursing will attend a random visit for approximately 20% (6) of the visits to observe the interaction, record conversational content using the ACP checklist, and, after the intervention and debrief visit are complete, will discuss observations with the PI and discuss ongoing adaptations to the checklist to align it with TIC principles.

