D5.3 Post-data collection procedures. After each time of data collection is complete, the KSP will facilitate the \$25 gift card incentive as a token of gratitude for each participant's time. This amount is in line with other studies operating at the study site. The study team will audit quantitative data within 1-2 days following data collection to ensure completeness and accuracy. If REDCap data collection was not possible during the interview, quantitative data will be entered into REDCap immediately. A copy of the paper survey will be scanned into the REDCap record, to promote data integrity, and then shredded. We will facilitate data transparency by sharing results with participants per their preference. Audio-recorded data will be professionally transcribed by Rev.com and securely stored.

D6. Limitations. This innovative single-arm, pre-post intervention study will include both qualitative and quantitative methods, gather preliminary data on initial efficacy and implementation outcomes, and will be a vital step for future work adapting our intervention and conducting larger studies assessing the effectiveness within marginalized communities. This study is limited by collecting data from a single arm, which does not allow for between group comparison, however, this approach is appropriate for introductory studies to explore within-group differences in efficacy outcomes and initial acceptability, feasibility, and adaptability of an ACP intervention. Face-to-face data collection methodology is subject to biased responses from social desirability and racial discordance, which will be handled by using trust-building techniques from instrument experts and community-engaged researchers (e.g., using community partnerships for recruitment, framing the participant as the expert informant, and asking for their help) [26, 27]. The mode of in-person, questionnaire delivery will assist participants with health or reading literacy challenges and prevent exclusion of participants with insufficient technology or transport [26]. The intervention delivery within the novel resiliency hub model will enable a safe, private, and supportive setting to explore planning needs and goals. Additionally, the strong community partnership, robust experience of the research team, and

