Activity	2024				2025			
	Q1	Q2	Q3	Q4	Q1	Q2	Q3	Q4
Protocol development								
IRB approval/renewal								
Prepare study database								
Team training								
Purchase gift cards and distribute								
Intervention and data collection								
Data analysis								
Manuscript preparation and dissemination								
Grant development and submission								

Table 2. Key Outcomes

Variable (Measure)	Time Period	Aim	Purpose
ACP Processes: ACP Processes Scale (15-items, 5-point Likert scale (1 = almost never, 5 = almost always, participants rate how often they participate in different ACP processes. Higher summed scores indicate higher participation in ACP processes, e.g., I review my advance care documents so that I know what they say))	Baseline, 30-day follow-up	Aim 1	This scale assesses the frequency of participation in ACP processes. We hypothesize that at 30-day follow-up $\geq 80\%$ of the participants will endorse ACP process scores as anticipated compared with $<80\%$ at baseline. Possible scores: 15-75 Anticipated scores at baseline: <37 ; at 30-day follow-up: ≥ 37
ACP Values/Beliefs: ACP Values and Beliefs scale (7-item, 5-point	Baseline, 30-day	Aim 1	This scale assesses ACP misconceptions. We hypothesize

Likert (1=strongly agree, 5=strongly disagree, lower scores=fewer ACP misconceptions)	follow-up	
that at 30-day follow-up at least 80% of participants will hold ACP misconceptions as anticipated compared with <80% at baseline.
 
Possible scores: 7-35
 
Anticipated scores at baseline: <28; at 30-day follow-up: ≥ 28

ACP Actions: ACP Stages of Change Scale (6-items, 5-point Likert (0=no, not at all, 4=yes, I've done that months or years ago, higher scores on individual items and overall=higher ACP participation)	Baseline, 30-day follow-up	
Aim 1
 
This scale indicates the stage of change (precontemplation to maintenance) that each participant is in for the six core ACP actions/behaviors. We hypothesize that at 30-day follow-up $\geq 80\%$ of participants will report ACP actions as anticipated compared with <80% at baseline.
 
Possible overall scores: 0-24
 
Anticipated overall scores at baseline: <14, at 30-day follow-up: ≥ 14
 
Possible scores for individual ACP actions: 0-4
 
Anticipated individual scores at baseline: 0-2, at 30-day follow-up: 3-4

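### Advance directive completion, the first-named Aim 1 action, is measured in the available text only by self-report to study staff; recording the form at Visits 2 and 3 would bound the bias

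*Combined protocol and SAP*

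**What the plan says.** - **Outcome.** Section A, Aim 1, includes among its efficacy outcomes "actions (e.g., advance directive completion, family conversations about life-sustaining measures". H1 gives the same examples.
- **Measure.** Section E, Table 2 (Key Outcomes), lists one instrument for actions: "ACP Actions: ACP Stages of Change Scale (6-items, 5-point Likert (0=no, not at all, 4=yes, I've done that months or years ago". Its stated purpose is: "This scale indicates the stage of change (precontemplation to maintenance) that each participant is in for the six core ACP actions/behaviors".
- **Standard.** At 30 days, at least 80% "of participants will report ACP actions as anticipated compared with <80% at baseline". The overall score is expected to go from below 14 to 14 or more, and each item from 0-2 to 3-4.
- **Mode.** Section D5.2: "During Visit 1 and Visit 3, the questionnaire will be administered to each participant in-person by the study team member". Participants have a copy of the questions and responses to refer to. Telephone is the fallback.
- **Session.** Under Section D2 the PI delivers the single Visit 2 session. "Participants will be offered the opportunity to complete an advance directive", and the protocol accepts that some will not be ready.
- **Entry.** Section D3 admits only residents without a completed directive.
- **Acknowledged bias.** Section D6: "Face-to-face data collection methodology is subject to biased responses from social desirability and racial discordance". The stated response is trust-building technique.
- **Literacy.** Section C: "Resident illiteracy was also major finding from these interviews and influenced the choice of investigator-administered study instruments".

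The available text does not say that a form completed at Visit 2 is recorded as outcome data, or that the participant is asked to show a form at Visit 3. The fidelity observers in Section D5.2 attend about six sessions and log conversational content.

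**The concern.** Among the Aim 1 examples, AD completion is the one that leaves a document. The study has two contacts at which that document could be noted: the PI leads the session in which it is offered, and Visit 3 is normally in person. The described plan relies instead on the participant's answer to a study team member, 30 days after the study itself offered the form.

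Two features of the design prevent an over-report from cancelling out. Eligibility requires no completed AD, so the baseline answer on an AD item should be low by design. There is also no control group in which the same tendency would appear. A false report of completion at 30 days therefore counts wholly as apparent improvement. Trust-building may make wrong answers rarer, but it cannot detect one. Section E intends the effect estimates to inform the powering of later work, so an inflated completion rate could carry into the next study.

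**Working it through.** **Figures in the plan that can be reproduced**
- Overall range of the actions scale (Table 2): 6 × 0 = 0 and 6 × 4 = 24. This matches the stated 0-24.
- Fidelity visits (Section D5.2): 0.20 × 30 = 6. This matches.
- Efficacy standard (Section E): 0.80 × 30 = 24 participants.
- N = 30 rests on feasibility, so there is no power calculation to reproduce.

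**Which standard is exposed**
- An AD item is one of six and contributes at most 4 of 24 points. Misreporting a 2 as a 3 moves the total by 1 point; misreporting a 0 as a 3 moves it by 3.
- The total of 14 can be reached with nothing on that item: five other items at 3 give 5 × 3 = 15.
- The overall score is therefore only weakly sensitive to a false AD report, and it cannot stand in for an AD count. The exposure lies mainly in the item-level proportion at 3-4.

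**Sensitivity to over-reporting**

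Let p be the true completion rate and f the share of non-completers who report completion. Both are assumptions; the documents give neither. Assume also that all 30 are followed up and that no completer under-reports.

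Expected self-reported rate = p + (1 − p) × f. For p = 0.60 and f = 0.30 this is 0.60 + 0.40 × 0.30 = 0.72.

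The chance of at least 24 of 30 is the upper binomial tail at that rate:

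| True rate p | f = 0 | f = 0.1 | f = 0.2 | f = 0.3 | f = 0.5 |
|---|---|---|---|---|---|
| 50% | 0.1% | 0.4% | 1.7% | 5.9% | 34.8% |
| 60% | 1.7% | 4.7% | 11.0% | 22.4% | 60.7% |
| 70% | 16.0% | 26.2% | 39.6% | 55.3% | 84.7% |
| 80% | 60.7% | 71.2% | 80.6% | 88.4% | 97.4% |

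**Over-reporting needed for the expected rate to equal 80%:** f = (0.80 − p)/(1 − p).
- p = 50%: 0.30/0.50 = 60%, or 9 of 15 non-completers.
- p = 60%: 0.20/0.40 = 50%, or 6 of 12.
- p = 70%: 0.10/0.30 = 33%, or 3 of 9.

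**The case against.** The strongest reply has five parts.

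1. **Inference.** The six actions are not listed and only the 0 and 4 anchors are given. That there is a distinct AD item, and that a 3 means a completed form, are inferred from the Aim 1 examples. That the PI would see a form completed at Visit 2 is inferred from the PI leading the session. This stands as a caveat. If there is no AD item, however, AD completion has no listed measure at all, and the case for a field is stronger.
2. **Missing material.** Figure 3 (activities by visit) and the questionnaire are not in the available text. A reader might infer that the plan makes no use of the document. The text supports only that no check is described.
3. **Size.** No over-reporting rate can be taken from the documents. At a true rate of 60%, f = 0.1 moves the chance of passing only from 1.7% to 4.7%. A resident also has less scope to claim falsely, to the same study, a form that the PI knows was not completed in session. This stands: the direction of any over-reporting bias is clear, the size is not.
4. **Literacy.** A reader might infer that residents cannot tell a partly filled form from a complete one. The illiteracy finding comes from five interviews with housing specialists, and the protocol answers it with staff-administered instruments. The documents do not show misreporting on this ground, so the point does not rest on it.
5. **Remedy.** Defining completion as observed forms only would count every form held by a decision-maker or provider, and every telephone follow-up, as a failure. Pressing residents to produce a document may also sit badly with a trauma-informed approach. Both points stand, and the fix is framed accordingly.

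It can also be said that a 30-person pilot that discloses the bias and uses validated scales needs no correction. That limits the weight of the point, but it is no reason to leave a cheap check undone.

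**Conclusion.** The point holds as a low-cost improvement to a named efficacy outcome. In the available text, AD completion is ascertained only by self-report, in a mode that the protocol itself calls bias-prone, and no document check is described at either contact where one is feasible. Over-reporting at 30 days would count as improvement because baseline completion is excluded by eligibility and there is no comparator.

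The effect falls mainly on the item-level 3-4 proportion. A reader might infer that the whole ACP Actions result is inflated, or that over-reporting would carry the trial past 80%. The documents support neither: the overall cut of 14 can be met without an AD, and the misreporting rate is unknown. Under the assumed true rate of 60%, over-reporting by 10-30% of non-completers raises the chance of reaching 24/30 from about 2% to about 5-22%. Larger or smaller effects follow from other assumed values. The conclusion also assumes that the scale has an AD item and that Figure 3 and the questionnaire contain no verification step.

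**What to change.** - **Visit 2:** add a REDCap yes/no field, filled in by the PI, for whether an AD was completed in the session.
- **Visit 3:** add one field with four values: form seen and complete; reported but not seen; none; not assessable because the contact was by telephone. Showing the form should be voluntary, and what counts as complete should be written down beforehand.
- **Keep** the Stages of Change scale and its standard unchanged.
- **Report** observed completion (Visit 2 or Visit 3) with its confidence interval as a lower bound, beside the self-reported proportion as an upper bound, which holds if no completer under-reports. Give the number of disagreements and draw the AD-completion conclusion from both figures.

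The cost is two fields and a request to have the form to hand, with no added visit. The downside is that forms held elsewhere and telephone follow-ups will be unseen, which is why the observed figure is a bound and should not replace the definition in H1.

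The document is dated 11/7/2025. If follow-up is already finished, tabulate Visit 2 completions from session records where these exist, and label the remainder as self-reported.
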